**Table 6-2 Criteria for interruption, delay, re-initiation and discontinuation of PDR001**

Worst toxicity CTCAE Grade (unless otherwise specified)	Recommended dose interruption, delay and discontinuation for PDR001 during a cycle of treatment
Infusion Reaction or Hypersensitivity reaction	
Grade 1	Decrease infusion rate until recovery of the symptoms
Grade 2	
Stop infusion immediately, and keep line open. Provide supplemental oxygen and fluids, as needed.
 
Monitor vital signs (e.g. blood pressure, pulse, respiration, and temperature) every 15 ± 5 minutes until resolution.
 
Administer medications for symptomatic relief as needed:
 
 
● Urticaria: Diphenhydramine (25 to 100 mg i.v.) as needed every 4 to 6 hours, or alternative as appropriate.
 
● Fever: Acetaminophen/paracetamol (650-1000 mg by mouth) as needed every 4 to 6 hours, or alternative as appropriate.
 
● Rigors: Meperidine 25 mg i.v. as needed every 6 hours or alternative as appropriate. Corticosteroids may be administered, as needed.
 
 
Resume infusion once infusion reaction resolves (within 8 hours of initial start of infusion):
 
Maintain dose level. Administer oral pre-medication (e.g. 1000 mg of acetaminophen/paracetamol, 50-100 mg diphenhydramine hydrochloride or alternative antihistamine), within 60 minutes of restarting the infusion.
 
Restart infusion at 50% of previous rate under continuous observation. Ensure that there is a minimum observation period of 1 hour prior to restarting the infusion.
 
If the AE recurs at the reinitiated slow rate of infusion, and despite oral pre-medication, then discontinue patient from study.

Grade 3 or Grade 4	
Discontinue infusion immediately, and discontinue patient from study.
 
Provide supplemental oxygen, fluids, and other resuscitative measures as needed. Monitor vital signs (e.g. blood pressure, pulse, respiration, and temperature) every 15 ± 5 minutes until resolution.

Neutropenia (ANC)	
Grade 3 (ANC < 1000 - 500/mm  )	Dose delay for PDR001-related Grade 3 until resolved to ≤ Grade 1
Grade 4 (ANC < 500/mm  )	Discontinue for PDR001-related Grade 4 > 7 days duration
Thrombocytopenia	
Grade 3 (PLT < 50,000 - 25,000/mm  )	
Dose delay for PDR001-related Grade 3 until resolved to ≤ Grade 1
 
Discontinue for PDR001-related Grade 3 > 7 days or associated with bleeding

Grade 4 (PLT < 25,000/mm  )	Discontinue for PDR001-related Grade 4
Febrile neutropenia	
(ANC < 1.0 x 10  /L, fever ≥ 38.5°C)	
Dose delay for PDR001-related Grade 3 until resolved to ≤ Grade 1
 
Discontinue for PDR001-related Grade 4

Worst toxicity CTCAE Grade (unless otherwise specified)	Recommended dose interruption, delay and discontinuation for PDR001 during a cycle of treatment
Lymphopenia	
Grade 3 (<0.5-0.2 x 10  /L)	Maintain dose and schedule for PDR001-related ≤ Grade 3
Grade 4 (<0.2 x 10  /L)	Dose delay for PDR001-related Grade 4 until resolved to ≤ Grade 3 PDR001-related Grade 4 lymphopenia or leukopenia does not require discontinuation
Renal See Appendix 4 “Renal Adverse Event Management Algorithm” for additional guidance on monitoring and management of any grade events	
Serum creatinine	
Grade 2 (> 1.5 - 3.0 x ULN) or Grade 3 (> 3.0 - 6.0 x ULN)	Dose delay for PDR001-related ≥ Grade 2 until resolved to ≤ Grade 1
Grade 4 (> 6.0 x ULN)	Discontinue for PDR001-related Grade 4
Liver See Appendix 4 “Hepatic Adverse Event Management Algorithm” for additional guidance on monitoring and management of any grade events	
AST or ALT	
Grade 2 (> 3.0 - 5.0 x ULN)	Dose delay for PDR001-related ≥ Grade 2 until resolved to ≤ Grade 1 Discontinue for concurrent AST or ALT >3x ULN and total bilirubin > 2x ULN
Grade 3 (> 5.0 - 20.0 x ULN) or Grade 4 (> 20.0 x ULN)	Discontinue for PDR001-related ≥ Grade 3 or Grade 4
Bilirubin*	
Grade 2 (> 1.5 - 3.0 x ULN)	Dose delay for PDR001-related ≥ Grade 2 until resolved to ≤ Grade 1 Baseline total bilirubin is within normal limits, delay dosing for PDR001-related Grade ≥ 2 toxicity Baseline AST/ALT or total bilirubin in the Grade 1 toxicity requiring dose delays for reasons other than a 2-Grade shift in AST/ALT or total bilirubin may resume treatment in the presence of Grade 2 AST/ALT or total bilirubin
Grade 3 (> 3.0 - 10.0 x ULN) or Grade 4 (> 10.0 x ULN)	Discontinue for PDR001-related ≥ Grade 3 or Grade 4
Asymptomatic amylase and/or lipase elevation**	
Grade 3 (> 2.0 - 5.0 x ULN) or Grade 4 (> 5.0 x ULN)	Any Grade ≥3 PDR001-related isolated amylase or lipase abnormality that is not associated with symptoms or clinical manifestations of pancreatitis does not require dose delay or discontinuation. The Novartis Medical Monitor should be consulted for such amylase or lipase abnormalities

Worst toxicity CTCAE Grade (unless otherwise specified)	Recommended dose interruption, delay and discontinuation for PDR001 during a cycle of treatment
Cardiac general	
Grade 2 or Grade 3	Dose delay for PDR001-related $\geq$ Grade 2 until resolved $\leq$ Grade 1 Discontinue for PDR001-related Grade 3 lasting $>$ 7 days
Grade 4	Discontinue for PDR001-related Grade 4
Endocrine See Appendix 4 "Endocrinopathy Management Algorithm" for additional guidance on monitoring and management of any grade events	
Grade 2 or Grade 3	Dose delay for any Grade $\geq$ 2 PDR001-related until resolved $\leq$ Grade 1 Grade 3 PDR001-related endocrinopathies adequately controlled with only physiologic hormone replacement do not require discontinuation
Grade 4	Grade 4 PDR001-related endocrinopathies, such as adrenal insufficiency, ACTH deficiency, hyper- or hypothyroidism, or glucose intolerance, which resolve or are adequately controlled with physiologic hormone replacement (corticosteroids, thyroid hormones) or glucose-controlling agents, respectively, may not require discontinuation after discussion with and approval from the Novartis Medical Monitor.
Skin Rash/photosensitivity See Appendix 4 "Skin Adverse Event Management Algorithm" for additional guidance on monitoring and management of any grade events.	
Grade 2	In presence of Grade 2 PDR001-related skin toxicity, treatment may be resumed (even if patient experience before a Grade 3 PDR001-related toxicity)
Grade 3 or Grade 4	Dose delay for PDR001-related Grade 3 until resolved $\leq$ Grade 1 Discontinue for PDR001-related Grade 3 lasting $>$ 7 days, or PDR001-related Grade 4
Stevens-Johnson syndrome (SJS), or Lyell syndrome/toxic epidermal necrolysis (TEN)	
Any Grade	Permanently discontinue study treatment.
Gastrointestinal See Appendix 4 "GI Adverse Event Management Algorithm" for additional guidance on monitoring and management of any grade events	
Diarrhea***	
Grade 2	Dose delay for PDR001-related Grade $\geq$ 2 until resolved $\leq$ Grade 1 or baseline
Grade 3 or Grade 4	Discontinue for any PDR001-related Grade 3 lasting $>$ 7 days, or PDR001-related Grade 4
Fatigue/Asthenia Fatigue/ Asthenia (General disorders and administration site conditions)	
Grade 3 or Grade 4	Dose delay for PDR001-related Grade 3 until resolved $\leq$ Grade 1 Discontinue for PDR001-related Grade 3 lasting $>$ 7 days, or PDR001-related Grade 4
Any Neurological toxicity See Appendix 4 "Neurological Adverse Event Management Algorithm" for additional guidance on monitoring and management of any grade events	
Grade 2	Dose delay for PDR001-related Grade $\geq$ 2 until resolved $\leq$ Grade 1

Worst toxicity CTCAE Grade (unless otherwise specified)	Recommended dose interruption, delay and discontinuation for PDR001 during a cycle of treatment
Grade 3 or 4	Discontinue for PDR001-related Grade 3 lasting > 7 days, or PDR001-related G4
Ocular (uveitis, eye pain, blurred vision)	
Grade 2	Dose delay for PDR001-related Grade $\geq$ 2 until resolved $\leq$ Grade 1 Discontinue for any Grade 2 PDR001-related uveitis, eye pain or blurred vision that does not respond to topical therapy and does not improve to Grade 1 severity within the re-treatment period OR requires systemic treatment
Grade 3 or Grade 4	Discontinue for Grade 3 PDR001-related uveitis of any duration Discontinue for PDR001-related Grade 3 lasting > 7 days, or PDR001-related Grade 4
Pulmonary (pneumonitis, bronchospasm)	
See Appendix 4 "Pulmonary Adverse Event Management Algorithm" for additional guidance on monitoring and management of any grade events.	
Grade 1	Patients with persistent Grade 1 pneumonitis after completion of a steroid taper over at least 1 month may be eligible for retreatment if discussed with and approved by Novartis Medical Monitor.
Grade 2	Dose delay for PDR001-related Grade $\geq$ 2 until resolved $\leq$ Grade 1
Grade 3 or Grade 4	Discontinuation for Grade 3 PDR001-related pneumonitis of any duration Discontinue for PDR001-related Grade 3 lasting > 7 days or PDR001-related Grade 4
Cytokine Release Syndrome (CRS)	
Grade 2 or Grade 3 or Grade 4	If CRS is suspected (very high fever and precipitous drops in blood pressure, myalgia, change in mental status) treat with corticosteroids.
Other Non-laboratory adverse events	
Grade 2	Dose delay for PDR001-related Grade $\geq$ 2 until resolved $\leq$ Grade 1
Grade 3 or Grade 4	Discontinue for PDR001-related Grade 3 lasting > 7 days, or PDR001-related Grade 4
Other laboratory adverse events	
Grade 3 or Grade 4	Dose delay for PDR001-related $\geq$ Grade 3 until resolved to $\leq$ Grade 1 Isolated Grade 4 electrolyte imbalances/abnormalities not associated with clinical sequelae and corrected with supplementation/appropriate management within 72hrs of their onset do not require discontinuation.

*Note: If Grade 3 or 4 hyper-bilirubinemia is due to the indirect (non-conjugated) component only, and hemolysis as the etiology has been ruled out as per institutional guidelines (e.g., review of peripheral blood smear and haptoglobin determination), then delay treatment until resolved <math>\leq</math> Grade 1 and continue treatment at the discretion of the investigator.
 
**Note: A CT scan or other imaging study to assess the pancreas, liver, and gallbladder must be performed within 1 week of the first occurrence of any <math>\geq</math> Grade 3 of amylase and/or lipase. If asymptomatic Grade 2 elevations of lipase and/or amylase occur for a second time, patients will be discontinued permanently from study treatment.
 
***Note: antidiarrheal medication is recommended at the first sign of abdominal cramping, loose stools or overt diarrhea.
	

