#### **6.2.3 Dose modifications and dose delay**

There will be no dose modifications allowed for PDR001.

All dose interruption, delay and discontinuation should be based on the worst preceding toxicity (CTCAE Version v4.03). If a patient experiences a Grade 3 PDR001-related AE, treatment with PDR001 should be interrupted unless otherwise specified in [Table 6-2](#). Refer to [Section 6.2](#) for Management of toxicities and immune related AEs. Following resolution of the toxicity to

Grade 1, patient may resume PDR001 treatment at the same dose level, if there is no evidence of disease progression.

A decision to resume treatment with PDR001 following the occurrence of a Grade 3 AE is at the discretion of the Investigator. If the investigator considers it to be in the patient's best interest to resume therapy before the toxicity has resolved to Grade 1, this may be permitted on a case by case basis, following discussion with Novartis.

If a patient experiences any Grade 4 PDR001-related AE, the treatment should be discontinued unless otherwise specified in [Table 6-2](#).

In case the infusion cannot be administered at the scheduled visit, it has to be administered as soon as possible. If the delay is between 1 and 7 days the procedures at the original schedule visit should be performed. If the delay is longer than 7 days, the procedure of the following visit should be performed.

Patients who missed 2 infusions plus 7 days should be discontinued from the study treatment and enter the Follow-up period. Exceptions may be made on a case by case basis after discussion between Novartis and the Investigator.

Patients who discontinue the study for an AE or clinically significant abnormal laboratory value must be followed as described in [Section 6.2](#).

All changes in study drug administration must be recorded on the Dose Administration Record eCRF.

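### Table 6-2 gives two re-start rules for PDR001 after a Grade 3 skin event that has fallen to Grade 2, and the visible text does not say which applies

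*Protocol*

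**What the plan says.** Three places in the protocol bear on re-starting PDR001 after a skin event.

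- **Table 6-2, Skin Rash/photosensitivity, Grade 2 row:** "In presence of Grade 2 PDR001-related skin toxicity, treatment may be resumed (even if patient experience before a Grade 3 PDR001-related toxicity" (the parenthesis closes there). No further condition is attached.
- **Table 6-2, same block, Grade 3 or Grade 4 row:** "Dose delay for PDR001-related Grade 3 until resolved" to Grade 1 or less. The row then adds: "Discontinue for PDR001-related Grade 3 lasting $>$ 7 days, or PDR001-related Grade 4".
- **Section 6.2.3:** "All dose interruption, delay and discontinuation should be based on the worst preceding toxicity". A PDR001-related Grade 3 event leads to interruption unless Table 6-2 says otherwise. PDR001 may be resumed once the toxicity has come down to Grade 1, at the investigator's discretion. If the investigator wants to "resume therapy before the toxicity has resolved to Grade 1, this may be permitted on a case by case basis, following discussion with Novartis".

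Table 6-2 also points to the Appendix 4 skin algorithm as additional guidance. That flow chart is not visible in the text available here.

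**The concern.** Table 6-2 is titled as covering re-initiation as well as interruption, so a site will look there to decide whether a patient may be dosed again. For a Grade 3 rash that has improved to Grade 2, one row opens dosing and the adjacent row keeps it closed. Section 6.2.3 gives a third answer: closed, unless agreed with the sponsor.

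Two things are at stake. The first is consistent safety management: two sites could treat the same patient differently and each point to the table. The second is how the event is recorded. SAP Section 2.4 tabulates study-treatment deviations, and SAP Sections 2.5.1 and 2.8.5 summarise dose interruptions and relative dose intensity. Resuming at Grade 2 without contacting the sponsor is permitted under one row and departs from the other row and from Section 6.2.3. Whether it counts as a deviation is therefore unclear, while protocol Section 12 allows no authorised deviations.

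**Working it through.** No arithmetic applies. The check is to take one test case through each instruction.

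**Test case.** A PDR001-related Grade 3 rash improves to Grade 2 within 7 days and is still Grade 2 when the next infusion is due. The 7-day limit comes from the Grade 3 or Grade 4 row: beyond it, or at Grade 4, the instruction is to discontinue and no re-start question arises.

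| Source | Answer for the test case |
|---|---|
| Table 6-2, skin, Grade 2 row | May resume; no condition stated |
| Table 6-2, skin, Grade 3 or Grade 4 row | Still delayed; Grade 1 or less not reached |
| Section 6.2.3 | Not before Grade 1, unless agreed case by case after discussion with the sponsor |

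**Can any visible text choose between them?**

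1. *Entering the table by worst grade.* The table's column heading and Section 6.2.3 both work by worst toxicity. That sends the patient to the Grade 3 row. The parenthesis in the Grade 2 row then has no effect for a prior Grade 3 skin event, although its words include one.
2. *The deference in Section 6.2.3 to Table 6-2.* The unless-otherwise-specified wording attaches to interruption at Grade 3 and discontinuation at Grade 4, not to the re-start grade. Read more broadly, it returns the reader to the two rows that differ.
3. *The word resumed in the Grade 2 row.* Resuming presupposes an interruption. The only delay instruction in the skin block is the one for Grade 3, so the natural reading of the Grade 2 row reaches the patients whom the next row still holds.
4. *The case-by-case route in Section 6.2.3.* It narrows the gap, because resumption before Grade 1 is possible. It does not close it: the Grade 2 row asks for no discussion with the sponsor.
5. *The bilirubin row of the same table.* It also allows resumption in the presence of Grade 2 values, but says who qualifies: patients whose delay had a cause other than the listed grade shift. The skin row has no such qualifier.

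None of these settles the test case.

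**The case against.** The strongest reply is that the two rows can be read so that both work. The Grade 2 row names skin toxicity in its first half, but the parenthesis refers to a Grade 3 PDR001-related toxicity without the word skin. It may mean a patient who was delayed for some other Grade 3 event and has a Grade 2 rash when ready to resume; the bilirubin row has that structure. It may also mean an earlier Grade 3 episode that had already resolved. A Grade 3 rash would then be handled only by the Grade 3 row. This reading is possible, so the text cannot be called an unavoidable contradiction. But neither limit is written, and a site following the plain words would not find it.

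The table column is headed as recommended action, the Grade 2 row uses may, and Section 6.2.3 leaves resumption to the investigator's discretion. That makes it a permission set against a delay instruction. The two still differ on whether dosing is open without sponsor discussion. The Appendix 4 skin algorithm may state the answer; that cannot be confirmed or excluded here.

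A reader might also infer more than the documents support:

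- *That the rule will be used often.* Section 6.2.2 lists skin among the sites most often involved in immune-related events, but describes those events as typically low grade and self-limited. No frequency of Grade 3 rash is given. According to the Amendment 06 study status, enrolment was complete and 12 patients remained on PDR001 at 21 May 2019.
- *That the conflict extends to SJS/TEN.* Those conditions have their own row, with permanent discontinuation at any grade, which is unaffected.
- *That the choice of row costs a full cycle.* Section 6.1.1 says a dose that cannot be given within a 7-day delay is skipped, whereas Section 6.2.3 says a missed infusion is given as soon as possible. These do not sit easily together, so no fixed loss of dose can be stated.
- *That the primary result is at risk.* PFS is centrally reviewed and analysed in the full analysis set. Nothing in the documents shows that this wording would alter it.

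**Conclusion.** The point holds as an unresolved inconsistency in a safety instruction. On plain wording, the two skin rows and Section 6.2.3 give incompatible answers for a PDR001-related Grade 3 rash that has fallen to Grade 2 within 7 days and remains there at the next infusion. The re-start thresholds differ by one CTCAE grade, and the instructions also differ on whether the sponsor must be consulted.

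The affected group is narrow and probably small; the documents give no count. The conclusion assumes that the parenthesis is read as written, with no unstated limit to non-skin or already resolved Grade 3 events, and that the Appendix 4 skin algorithm does not already settle the matter. It implies no view on which threshold is right.

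**What to change.** The sponsor should reconcile the two skin rows of Table 6-2, Section 6.2.3 and the Appendix 4 skin algorithm so that:

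- one re-start rule applies after a PDR001-related Grade 3 skin event;
- the text states which prior Grade 3 events the parenthesis covers (skin or other, ongoing or resolved);
- the text states whether discussion with the sponsor is required before resuming.

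The threshold is for the sponsor to decide. The cost is a revised table row and a matching sentence in Section 6.2.3, by clarification letter or with the next amendment. No change to the sample size or the analyses is needed.

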#### **6.2.4 Management of toxicities and immune related AEs (irAEs)**

All the patients whose treatment is interrupted or permanently discontinued due to an AE or clinically significant laboratory value, must be followed-up at least once a week (or more frequently if required by institutional practices, or if clinically indicated) for 4 weeks, and subsequently at approximately 4-week intervals, until resolution or stabilization of the event, whichever comes first. Appropriate clinical experts should be consulted as deemed necessary. In case of suspected irAEs, the relevant immunological assessments (e.g. rheumatoid factor, anti-DNA Ab, etc.) should be performed.

Algorithms have been provided to assist investigators in assessing and managing the following groups of irAEs: Gastrointestinal; Renal; Pulmonary; Hepatic; Endocrinopathy; Skin; and Neurological. Management Algorithms can be found in the [Appendix 4](#).

For non- immune related AE as Grade 1 or 2, treatment with PDR001 maintains dose and schedule unless it specifies in the [Table 6-2](#).

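### Table 6-2 inverts severity for asymptomatic amylase/lipase elevation: a second Grade 2 value ends PDR001 permanently, while isolated PDR001-related Grade 3-4 values need no delay or discontinuation

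*Protocol*

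**What the plan says.** Protocol Table 6-2 has a row for asymptomatic amylase and/or lipase elevation. It covers two grade bands only, "Grade 3 (> 2.0 - 5.0 x ULN) or Grade 4 (> 5.0 x ULN"), and has no Grade 2 line. For any isolated PDR001-related value in those bands, the row says that one without symptoms or clinical manifestations of "pancreatitis does not require dose delay or discontinuation". It adds: "The Novartis Medical Monitor should be consulted for such amylase or lipase abnormalities".

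The double-asterisk footnote on that row has two parts. First, imaging of the pancreas, liver and gallbladder "must be performed within 1 week of the first occurrence of any" elevation of Grade 3 or higher. Second: "If asymptomatic Grade 2 elevations of lipase and/or amylase occur for a second time, patients will be discontinued permanently from study treatment". This second part is not limited to PDR001-related events and makes no exception through the Medical Monitor.

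Two general rules surround the table. Under Section 6.2.3, after a Grade 3 PDR001-related event, "treatment with PDR001 should be interrupted unless otherwise specified in" Table 6-2; the Grade 4 rule in that section carries the same exception. Under Section 6.2.4, for non-immune-related Grade 1 or 2 events only, treatment "maintains dose and schedule unless it specifies in the" Table 6-2.

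**The concern.** A dose-modification table should not act more severely on a milder grade of the same abnormality unless it gives a reason. Here a patient with a second symptomless value of at most 2.0 x ULN must come off PDR001 for good. A patient with an isolated, symptomless, PDR001-related value above 5.0 x ULN may continue after consultation and imaging.

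For an affected patient the stake is permanent loss of study treatment, in a population that Section 1.2 describes as having a poor prognosis whatever second-line treatment is used. For a site the stake is compliance. Section 12 permits no authorised deviations, and SAP Section 2.4 tabulates failure to discontinue after meeting withdrawal criteria. An investigator who handled a repeat Grade 2 value as the row handles Grade 3 could therefore be recorded as deviating.

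**Working it through.** The plan gives no figure to reproduce, so the check compares text and adds two simple counts.

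1. **Grade boundaries.** The row starts Grade 3 above 2.0 x ULN and Grade 4 above 5.0 x ULN. Grade 2 is therefore at most 2.0 x ULN.

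2. **Actions side by side**, for symptomless elevations:

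| Finding | Source | Action as written |
|---|---|---|
| Second Grade 2 (at most 2.0 x ULN) | Footnote, last sentence | Permanent discontinuation |
| Isolated PDR001-related Grade 3 (above 2.0 to 5.0 x ULN) | Row, and footnote on imaging | No delay or discontinuation required; Medical Monitor consulted; imaging at first Grade 3 or higher value |
| Isolated PDR001-related Grade 4 (above 5.0 x ULN) | Same | Same |

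3. **Reconciling text.** The Grade 3 and Grade 4 rules of Section 6.2.3 yield to the table. So does the Grade 1-2 default of Section 6.2.4, which in any case covers only non-immune-related events. Section 7.1.3 lists an adverse event among reasons for which treatment may stop, and lists only death and pregnancy as reasons for which it must. That does not settle the conflict, because Table 6-2 imposes mandatory stops of its own, such as for SJS/TEN. Appendix 4 has no pancreatic algorithm.

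4. **Other rows.** Stopping at Grade 2 is not unusual in this table. For a Grade 2 infusion reaction: "If the AE recurs at the reinitiated slow rate of infusion, and despite oral pre-medication, then discontinue patient from study". Some Grade 2 ocular events also lead to stopping. In both rows the higher grades lead to stopping too: Grade 3-4 infusion reactions; Grade 3 uveitis of any duration, other Grade 3 ocular events lasting more than 7 days, and Grade 4. No other row treats a lower grade more strictly than a higher one.

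5. **Reach.** Neither test is in Protocol Table 7-6. SAP Table 2-4 has 7 + 13 = 20 entries and SAP Table 2-5 has 4 + 9 + 2 = 15, so 35 in total, of which amylase or lipase account for 0. On 21-May-2019 (Amendment 06, study status), 12 patients were still on PDR001: 12/122 = 9.8% of all randomised. Eleven of them were in the PDR001 arm (11/82 = 13.4%) and one had crossed over.

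**The case against.** The strongest reply is that there is no contradiction. The two sentences govern different grades, the row is permissive and does not forbid stopping, and the column is headed as a recommendation. This stands as far as it goes. A reader might infer that Table 6-2 gives opposite orders for the same value, and it does not. What remains is an inverted severity order. The footnote is worded as a mandate, so the column heading does not soften it.

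A second reply is that the row's exemption may not reach repeat events, since isolated is undefined and could mean non-recurrent. It could equally mean without other findings. The inversion does not depend on this: even a first Grade 4 value needs no delay, whereas a second Grade 2 value ends treatment.

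A third reply is that deleting a stopping rule is the less cautious choice when the documents do not show which sentence is wrong. That is fair, so outright deletion should not lead the recommendation. A reader might also assume that Grade 2 is simply a misprint for a higher grade. The documents do not establish that. If it were so, the footnote would conflict directly with the row, and both would need correction.

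Finally, little practical consequence is shown. That is accepted and sets the severity. The 9.8% is a late snapshot of patients on PDR001 and does not measure how many were subject to the rule during the trial.

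**Conclusion.** The point holds as a severity inversion within Table 6-2, at minor severity. As written, the mildest grade addressed carries the only mandatory permanent stop, and nothing else in the protocol resolves this.

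Its reach is very small. The scheduled panel would not detect these elevations, and the SAP's laboratory tables list neither test. This does not prove that no test was done, since Section 7.2.2.5 allows unscheduled evaluations. SAP Section 4.1 says that the vast majority of patients had stopped treatment by the start of the pandemic. The documents give no rate of repeat Grade 2 elevation and identify no affected patient.

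A reader might infer that patients were wrongly withdrawn or that the efficacy comparison is distorted. The documents support neither. The primary analysis keeps patients as randomised in the FAS, and no endpoint definition or sample-size figure refers to this rule. The effect is on patient management only.

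The conclusion assumes that the footnote's Grade 2 follows the row's cut-offs.

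**What to change.** Replace the last sentence of the double-asterisk footnote so that a repeat asymptomatic Grade 2 amylase or lipase elevation prompts Medical Monitor consultation and no longer requires permanent discontinuation. Grade 2 is then handled no more strictly than Grade 3 or above. Investigators can still stop treatment for an adverse event under Section 7.1.3.

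The sponsor's medical team should confirm which grade was intended. If it was a higher one, correct the grade in the footnote and align the Grade 3-4 row with it, so that the two do not conflict directly.

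The cost is one sentence, plus the matching row if a higher grade was meant. Under Section 12.1 it must be carried in a written amendment approved by the sponsor, the ethics committees and, where required, health authorities. It needs no new tests, visits or analyses, and no change to Table 7-6 or the SAP.
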